### Assessment of safety

The nurse intervention reflects recommended best practice involving ULTs that are recommended and licensed for this purpose. Participants will report any adverse events to the nurse. If benzbromarone is prescribed recommended checking of blood liver function tests will be undertaken.

### Procedures for missing, unused and spurious data

If participants leave the study for any reason or if there are omitted data we will use multilevel models for any missing outcome measures and an intention to treat (ITT) analysis.

### **Definition of populations analysed**

All patients randomised into the study will be analysed using an ITT analysis and LOCF for any missing data.

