# Statistical methods Intention to treat (ITT) analysis will be undertaken to compare treatment effects between groups. Multi-level models will be used to handle any missing outcome measures. Chi-square test will be used for dichotomous or categorical data and ANOVA test will be used for continuous variable. Adjustment will be made for baseline co-variables as appropriate using multiple regression models. Cost per quality adjusted life year (QALY) will be estimated.

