The nurse will follow up the patient at variable time intervals as appropriate to the needs of the patient. It is envisaged that visits will be most frequent (e.g. monthly) in the first 6 months when ULT is being initiated and titrated upwards; subsequently visits may reduce to 3, 6 or 9 monthly depending on difficulty of gout management. Telephone contact to review blood test results and to agree any required action can substitute for visits, and home visits for blood tests and advice are permitted if more convenient (e.g. elderly patients). If home visits are undertaken this will be done in accordance with the University of Nottingham fieldwork guidelines. If the nurse requires any advice concerning treatment strategy (e.g. in patients with serious or multiple co-morbidity, taking multiple drug treatments, or experiencing side-effects) this will be offered by Academic Rheumatology ([name] or, in his absence, another designated Rheumatologist – [name], [name] or [name]). All contacts with the patient (practice visit, home visit, telephone call) and for doctor advice will be logged (date, duration) for subsequent cost effectiveness analysis. Participants will be given a diary to keep during the 2 year study period in which they will record the date and duration of acute attacks of gout.

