### **B] Control/Standard Care arm**

Participants randomised to this group will have one consultation appointment with the research nurse. At this appointment they will be assessed by the nurse (identical enquiry, examination and investigations as above) and be provided with the Arthritis Research UK gout information booklet and a diary to prospectively document their acute attacks (frequency, duration, medical advice sought, medications taken, absence from work). The discussion will focus on the management of acute attacks and not on long-term management. In addition, they will be asked to provide a blood sample to check their SUA level at baseline, 12 months and 24 months, and complete a QOL questionnaire at 12 months (a new diary will be given at this point) and 24 months. This standard care group of participants will remain under the care of their general practitioner.

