### **STATISTICS**

### Methods

The trial statistician ([name]) will oversee the data management, evaluation and analyses. The database will be developed in collaboration with the CTU using access and analysed using SPSS. SUA will be analysed at baseline, 12 months and 24 months. Comparison will be undertaken between the nurse led intervention and control at each observational point. There will be no interim analyses for efficacy or safety. Intention to

Page **19** of **29** Final version 8 –18 May 2015

treat (ITT) analysis will be undertaken to compare treatment effects between groups. Multilevel models will be used for any missing outcome measures. Chi-square test will be used for dichotomous or categorical data and ANOVA test will be used for continuous variables. Adjustment will be made for baseline co-variables as appropriate. Cost per QALY will be estimated from the SF6D and the direct and indirect costs related to gout and its management.

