# A community based randomised controlled trial comparing nurse-led intervention with standard care

# -Analysis plan

Synopsis of the design: A 2 year community based randomised controlled trial will be undertaken in Nottingham to investigate clinical effectiveness and cost-effectiveness of a nurse-led quality of care intervention versus standard of care control. A questionnaire survey will be undertaken in the GP practices in Nottinghamshire to obtain 724 patients with gout according to the American College of Rheumatology (ACR) criteria and at least one acute attack in the past year. They will be randomly allocated to the intervention and the control group using stratified (according to the participated GP practices), block (fixed block of 4 for random allocation to keep the balance between the groups) randomisation method. Participants will be examined at baseline, 12 months and 24 months for outcomes such as serum uric acid (SUA), number of acute attacks in the previous year and quality of life (QoL) (SF36).

Principles of analysis: Intention to treat (ITT) analysis will be conducted. Descriptive analysis on raw differences between groups at baseline, 12 months and 24 months will be undertaken. Multi-level regression model (MLM) will be used for the overall comparison of the treatment effect between groups with repeated measures and missing data. We shall include all data from 3 time points in the same model, with repeated measures as level 1 units and individuals as level 2 units. The treatment group and time points will be considered as covariates in the model together with covariates at baseline for the adjustment purpose. Continuous data (eg, SUA, QoL score, etc) will be analysed using MLM linear regression, whereas dichotomous and categorical data will be analysed using MLM logistic or multinomial models. Comparison will be made between the intervention and the control in the RCT, as well as between the control in the RCT and the observational group.

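### Protocol version 8 gives two incompatible rules for missing outcomes, multilevel models and LOCF, and LOCF does not suit the year-2 endpoints

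*Supplement*

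**What the plan says.** Protocol version 8 (May 2015) deals with missing outcomes in four places.

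- Synopsis, Statistical methods: "Multi-level models will be used to handle any missing outcome measures".
- Statistics, Methods: "Multilevel models will be used for any missing outcome measures".
- Procedures for missing, unused and spurious data: "we will use multilevel models for any missing outcome measures and an intention to treat (ITT) analysis".
- Definition of populations analysed, the section that follows directly: "All patients randomised into the study will be analysed using an ITT analysis and LOCF for any missing data".

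The analysis plan, under Principles of analysis, adopts a multilevel regression model "for the overall comparison of the treatment effect between groups with repeated measures and missing data", fitted to three time points, and does not mention LOCF. The supplement dates that plan to 17 July 2013, and it still gives the target of 724 patients. Version 8 is later and keeps the LOCF sentence, so date order does not settle the matter in favour of the plan.

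The primary endpoint is the share of patients at the SUA target at the end of year 2. Reduction in attack frequency in the second year is a secondary endpoint.

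**The concern.** The two rules cannot both apply to the same missing value. A likelihood-based multilevel model uses what was observed and fills nothing in. LOCF writes a value into the empty cell and analyses it as if it had been measured. The LOCF clause covers any missing data, so it reaches the primary endpoint. The trial is open-label, and a choice between two written rules should not stay open until the data are seen.

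LOCF also fits these endpoints badly.

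- **SUA.** It is treated by upward titration, so an earlier value stands for a different stage of care from year 2.
- **Attacks.** LOCF would put a pre-trial or year-1 count into the second-year window. A carried-forward pre-trial count scores as no reduction by construction.
- **Precision.** Filled-in values are counted as observed, so standard errors come out too small.

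**Working it through.** **Inputs**

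- Planned dropout d = 10%, with 233 completers plus 23 dropouts per arm (Power calculations). The synopsis prints 36 dropouts, which does not add up to its own 256 per arm, so 23 is used here.
- On-treatment share at target: 92%, the phase 1 result at one year (Background). Alternative: 77%, since 23% of survey patients on urate-lowering therapy (ULT) were above 360 µmol/L (Power calculations).
- Share at target without ULT: 25%, since 75% of those patients were above 360 µmol/L. This also serves as a proxy for baseline and for controls.
- True year-2 share at target among nurse-arm leavers: not in the documents. Assumed range 25% to 75%, the lower end being the off-ULT survey level.

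**The plan's own figure.** 233 + 23 = 256 per arm, 512 in total. Inflating 233 for 10% loss gives 233/0.90 = 259, or 233 × 1.10 = 257 (both rounded up). The stated 256 is close to both.

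**Formula.** Bias in the nurse arm = d × (share at target carried forward - true year-2 share among leavers). In controls the carried and true shares are both taken as 25%, so their bias is zero.

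**Case A: lost after month 12, on-treatment value carried.**

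| Carried | True 25% | True 50% | True 75% |
|---|---|---|---|
| 92% | 0.10 × 0.67 = +6.7 points | +4.2 | 0.10 × 0.17 = +1.7 |
| 77% | 0.10 × 0.52 = +5.2 points | +2.7 | +0.2 |

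With 92% carried and 25% true, the LOCF difference is 92 - 25 = 67.0 points. The true difference is 0.90 × 92 + 0.10 × 25 - 25 = 60.3 points. The number needed to treat is 1/0.670 = 1.49 under LOCF against 1/0.603 = 1.66.

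**Case B: lost before month 12, baseline carried.**

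- True share 25%: 0.10 × (0.25 - 0.25) = 0.
- True share 75%: 0.10 × (0.25 - 0.75) = -5.0 points, that is, against the nurse arm.

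The baseline proxy may be low, because some entrants will already be on ULT. The whole-survey share is 0.30 × 77 + 0.70 × 25 = 40.6%, and against a true 75% that gives -3.4 points. The sign holds as long as leavers do better at year 2 than they did at baseline.

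**Standard errors.** If 23 filled-in values per arm add no real information, the standard error is understated by the factor √(233/256) = 0.95, about 5%. This matters most for quality of life, which the Power calculations section powers at only 80%.

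**Significance of the primary endpoint.** Take the worst case at 10% dropout: every nurse-arm leaver fails and every control leaver succeeds. The nurse arm is then 0.90 × 92 = 82.8% and control 0.90 × 25 + 10 = 32.5%, a difference of 50.3 points. With 256 per arm, power is about 100%, and it remains so with 77% in place of 92%.

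**The case against.** A reader might infer a stronger point: that LOCF is bound to favour the nurse arm because only that arm has frequent SUA tests. For nurse visits the protocol says "It is envisaged that visits will be most frequent (e.g. monthly) in the first 6 months when ULT is being initiated and titrated upwards", while controls are asked to "provide a blood sample to check their SUA level at baseline, 12 months and 24 months". The documents do not support that reading. Statistics, Methods limits the analysed SUA to baseline, 12 and 24 months, the analysis plan uses three time points, and the study-regimen table lists the same SUA times for both arms. Serial SUA appears only under Compliance, as a check on adherence to ULT. Nothing says that titration values may be carried forward. On the scheduled values the direction is open, as Case B shows.

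The top of Case A also needs every leaver to be at target when last measured and then to fall back to the off-ULT level. The listed reasons for leaving (moving away or changing practice, withdrawing consent, losing capacity) do not imply stopping ULT, and the GP is kept informed of changes to gout medication. On the other side, ULT prescriptions are issued through the study's hospital pharmacy, so leaving may interrupt supply. The documents do not settle which prevails, so a range is needed.

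A further objection is that a multilevel model assuming data missing at random would share most of the Case A bias: it too would predict a late leaver with a good month-12 value to be at target. For early leavers it would predict from the nurse-arm course and could be more favourable to the nurse arm than LOCF. This stands. The figures above describe the error of LOCF under stated assumptions, not the gain from removing it.

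Finally, the synopsis, Methods, missing-data section and analysis plan agree, and one clause under a populations heading does not. That shows which way to reconcile them, but no text gives the majority precedence.

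**Conclusion.** Wrong as written, and should be fixed. The contradiction is certain, sits in the current version, and is not resolved by the analysis plan.

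The size of the LOCF bias is conditional. At 10% dropout it is about +2 to +7 points in the nurse arm when 92% are carried forward as at target and 25% to 75% truly are. It is zero to about -5 points when a baseline of about 25% is carried forward and 25% to 75% are truly at target. The 75% is assumed throughout, and both the timing of dropout and the continuation of ULT after leaving are unknown. A one-way bias in favour of the intervention is not established.

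The finding of a difference on the primary endpoint is not at risk on the plan's own figures. What moves is the size of that difference and the number needed to treat, together with the year-2 attack result and the precision of the quality-of-life comparison.

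**What to change.** 1. In Definition of populations analysed, delete the LOCF clause and keep the statement that all randomised patients are analysed by intention to treat.
2. Name the multilevel model of the missing-data section and the analysis plan as the primary analysis. State that only 0-, 12- and 24-month values enter it, in both arms.
3. Add one sensitivity analysis that counts a missing 24-month SUA as not at target in both arms, because the primary model shares the bias if late leavers relapse unobserved. With 10% missing per arm and the figures above, it gives 0.90 × 92 = 82.8% against 0.90 × 25 = 22.5%, a difference of 60.3 points.

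The cost is one deleted clause, one added sentence and one extra analysis run. The nurse-arm success rate may look somewhat lower in the sensitivity analysis. No trial procedure changes.

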### **ADVERSE EVENTS**

The nurse intervention which is being tested in this study reflects recommended best practice and utilises ULT that is recommended and licensed for this purpose. Therefore, the occurrence of adverse events as a result of participation within this study is not expected and no adverse event data will be collected.

Self- reported adverse events in participants in the nurse intervention will be recorded and if judged to be due to ULT the drug will be stopped and an alternative ULT considered (i.e. as recommended in current guidelines). Known side effects of ULT (e.g. allopurinol, febuxostat, benzbromarone) will be reported to the MHRA using the Yellow Card system, in line with recommended practice, but will not be classed as adverse events with respect to the intervention and will therefore not be reported to the NRES as such. However, a summary of the side effects reported using the Yellow Card system will be included in the final summary submitted to NRES. Adverse events that are unrelated to the nurse intervention

Page **21** of **29** Final version 8 –18 May 2015

and ULT will be treated by the participant's general practitioner, as usual, and again not be reported to the REC.

To ensure clinical governance if the nurse is unsure of causality with respect to ULT she can involve the opinion of [name] (or in his absence [name], [name] or [name]).

Adverse events occurring in the standard care group will be assessed and managed as part of normal care by the general practitioner and will not be reported to the REC.

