### **Secondary endpoints:**

Percentage with reduction of frequency of acute attacks in the second year. Difference in QOL scores for SF36 and GAQ at end of study.

Percentage with reduction in size of the largest index tophus and reduction in number of tophi.

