### TRIAL / STUDY TREATMENT AND REGIMEN

The total study duration will be 3 years (8 month recruitment period, 2 years participation, 4 months analysis and writing up).

All appointments with our research nurses will be at the participants' local GP practice or in the participants' own home.

The study regimen is summarised in the table below (see also appendix1):

	RCT – nurse	RCT – control/
	intervention	standard care arm
Enquiry: age, sex, gout history, drug history, family history,	Х	X
comorbidities		
Individualised advice on management of acute attack	X	X
(selecting from ice packs, oral colchicine, oral NSAID plus		
PPI, corticosteroid).		
Provision of Arthritis UK patient booklet.	X	X
Tophi assessment (sites), if present	X	X
A clear verbal explanation of gout	X	
Individualised explanation of relevant risk factors	X	
Individualised advice on ways to reduce uric acid levels by	Х	
lifestyle modification, if appropriate		
Advice on ULT	X	
Height and weight (BMI)	X	X
Baseline/recruitment questionnaire (incl. SF36 & GAQ)	X	X
Serum uric acid, GFR and creatinine	X	X
Diary of acute attacks	X	X
Record of visits to GPs re gout management		X
SF36 'Quality of life' forms during acute attacks	Х	Х
12 month SUA	Х	X
12 month GFR & creatinine	Х	Х
12 month questionnaire (incl. SF36 & GAQ)	Х	X
12 month weight	Х	X

Page **15** of **29** Final version 8 –18 May 2015

24 month bloods	Х	X
24 month questionnaire (inl. SF36, GAQ, joint pain,	X	X
stiffness & function, gout attack triggers)		
24 month blood pressure	X	X
24 month weight	Х	Х

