# 2. Secondary outcomes

- Number of acute attacks in preceding year, year 1 and year 2 within each group and between groups
- Number of patients with tophi at baseline, 12 months and 24 months with each group and between groups
- Mean QoL scores (overall, different domain scores of SF36 and the Gout
   Asssessment Questionnaire (GAQ) including the Gout Impact Scale (GIS) of the GAQ.
   at 0, 12 and 24 months within each group and between groups
- Mean change of QoL scores from baseline to 12 months and 24 months within each group and between groups

**Covariates and baseline predictors:** age, gender, body mass index, disease duration, tophi, associated comorbidity etc.

Task allocation and timetable: The Nottingham CTU will undertake randomisation, development of the database for RCT and the web-based data entry platform. CTU will also conduct data monitoring and quality control for the RCT data. Academic Rheumatology will recruit patients, enter the data through a web-based data entry platform for the RCT data and develop an independent database for the observational group. Both datasets are not open for any interim analysis between baseline and 24 months to keep the randomisation. Analysis will start after 24 months when the data has been fully completed, quality checked over and closed. Analysis for clinical effectiveness (efficacy and side effects) will be completed in 3 months after the closing date of the data. Analysis for cost-effectiveness will be completed in 12 months, as it requires acquisition of additional data for cost. In brief:

- Recruitment 8 months
- RCT and observation 24 months
- Results for clinical effectiveness 3 months
- Results for cost-effectiveness 12 months

Economic Analyses Plan.

Two economic analyses are planned: the first being an economic analysis alongside the RCT and the second modelling the costs and benefits over a longer time horizon. The base case in both models would use an NHS perspective, with a societal perspective (that include indirect costs such as lost productivity) being undertaken in a sensitivity analysis.

Economic analysis alongside the RCT

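### The adverse-event text contradicts itself and, as written, yields side-effect data in the nurse arm only; follow-up tophus measurement is undated in both arms

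*Supplement*

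**What the plan says.** **Adverse events (protocol version 8).** The Adverse Events section opens by saying that "the occurrence of adverse events as a result of participation within this study is not expected and no adverse event data will be collected". The paragraph after it keeps events for one arm: "reported adverse events in participants in the nurse intervention will be recorded". For controls it says: "Adverse events occurring in the standard care group will be assessed and managed as part of normal care by the general practitioner". No step is described by which those events reach the trial.

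Four other places bear on this:
- Safety endpoints are declared not applicable.
- Assessment of safety has participants, with no arm named, reporting adverse events to the nurse.
- Trial Conduct includes adverse-event recording and reporting among the items audited.
- The analysis plan of July 2013, in its timetable, says: "Analysis for clinical effectiveness (efficacy and side effects) will be completed in 3 months".

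**Tophi.** The protocol's secondary endpoint is "Percentage with reduction in size of the largest index tophus and reduction in number of tophi". The analysis plan lists a different quantity: "Number of patients with tophi at baseline, 12 months and 24 months with each group and between groups". The study regimen table has one row, "Tophi assessment (sites), if present", ticked for both arms with no time point. The assessment text under the nurse intervention gives the calliper method, also without times.

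**Control-arm contact.** Controls "will have one consultation appointment with the research nurse", and the Synopsis likewise gives them a single contact at baseline. The regimen table nevertheless ticks weight at 12 and 24 months and blood pressure at 24 months for controls.

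**The concern.** The nurse-led package includes starting urate-lowering drugs and titrating them upwards. A reader of the results will ask whether this caused harm relative to usual care. If events are written down in one arm only, by nurses who see those patients repeatedly, there is no comparator. A count from the nurse arm could then neither show excess harm nor rule it out. The text does not settle even that much, because one sentence says nothing will be collected. Site staff, auditors and the analyst could each follow a different section and all be within the protocol.

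The tophus issue is similar but smaller. A reduction in size or number needs a baseline and a later measurement of the same patient. If the later one is not scheduled, it may be done at some nurse-arm visits and missed in controls, so the between-group comparison would rest on uneven data.

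**Working it through.** The plan states no figure on this point. The check sets the sections side by side, by arm and time.

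**1. Adverse events**

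| Source | Nurse arm | Control arm |
|---|---|---|
| Adverse Events, first paragraph | none collected | none collected |
| Adverse Events, later paragraphs | self-reports recorded | managed by the GP; no recording described |
| Assessment of safety | report to nurse | report to nurse |
| Control/Standard Care arm; Synopsis | – | one nurse contact, at baseline |
| Safety endpoints | not applicable | not applicable |
| Trial Conduct | recording audited | recording audited |
| Analysis plan, timetable | side effects analysed | side effects analysed |

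The first two rows cannot both be followed for the nurse arm. For controls, reporting to the nurse cannot work after baseline if there is only one consultation. The last two rows presuppose data that the first row says will not exist.

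**2. Opportunity to report**

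The nurse-intervention text envisages monthly visits for the first 6 months, then visits every 3, 6 or 9 months. It gives this as an expectation, with telephone contact allowed instead. Assuming that pattern over 24 months, the contacts after baseline in the nurse arm are:
- first 6 months: 6
- remaining 24 − 6 = 18 months: 18/3 = 6, 18/6 = 3 or 18/9 = 2
- total: 6 + 2 = 8 to 6 + 6 = 12

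Controls have 0 under the single-contact text. They have at most 2 if the 12- and 24-month weight and blood pressure entries mean a visit. Even if controls' spontaneous reports were written down, the chance of being heard would differ by arm.

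**3. Tophi**

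| Time | Schedule, nurse arm | Schedule, control arm | Analysis plan |
|---|---|---|---|
| Baseline | undated row, ticked | undated row, ticked; examined at the single appointment | compared |
| 12 months | no tophus row | no tophus row | compared |
| 24 months | no tophus row | no tophus row | compared |

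The dated rows cover bloods, questionnaires and weight, plus blood pressure at 24 months. The gap is in both arms.

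**4. Definition of the tophus outcome**

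The protocol counts patients whose index tophus shrinks or whose number of tophi falls. The analysis plan counts patients who have tophi. A patient whose index tophus halves but is still present is a success under the first and shows no change under the second. Size does not appear in the analysis plan.

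**The case against.** The strongest reply is that no comparative safety analysis was intended. Safety endpoints are not applicable, the drugs are described as licensed and recommended, and nurse-arm reports have a descriptive use: Yellow Card reporting and a summary for the ethics service. The analysis plan mentions side effects once, in a timetable clause, and lists no such outcome, method or group comparison. This stands against a reading that a reader might infer, namely that the plan promises between-arm side-effect results. It does not. The contradiction within the Adverse Events section remains, as does an analysis for which the protocol gives no consistent data source.

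A second reply is that controls are not wholly unobserved. The log of changes adds a question on new medical conditions to the 24-month questionnaire, which both arms receive. Practices check controls' status at one and two years, and health care use during attacks is costed in both arms. This is true, but none of it is adverse-event collection.

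On tophi, a reader might infer that the comparison is impossible because controls are seen once. The documents do not support that. The regimen table foresees weight and blood pressure for controls at follow-up, and the analysis plan has participants examined at 12 and 24 months. Appendix 1, to which the table refers, is not readable in the copy reviewed and may give the dates. The measurement is undated rather than excluded, in the nurse arm as much as in controls.

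**Conclusion.** The point holds in two parts.

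**Main part.** The Adverse Events section contradicts itself and does not fit Assessment of safety, Trial Conduct or the analysis plan's timetable. Followed as written, side-effect data would come from the nurse arm alone, with about 8 to 12 contacts after baseline against 0 to 2 under the assumptions shown. Such data can describe the nurse arm. They cannot support a statement that nurse-led care is safer, as safe or less safe than usual care. No event rate is given, so the size of any bias cannot be calculated.

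**Secondary part.** The tophus endpoint and the planned 12- and 24-month comparison have no dated follow-up measurement for either arm in the readable schedule. The single-contact text for controls conflicts with that schedule, and the two documents define the outcome differently. The number affected is the number of patients with tophi at baseline, which the documents do not give. This part rests on the readable text and would weaken if Appendix 1 dates the examinations.

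The primary serum uric acid outcome is untouched by either part.

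**What to change.** **Adverse events**
- Delete the clause saying that no adverse-event data are collected. Reconcile Safety endpoints, Assessment of safety, Adverse Events, Trial Conduct and the analysis plan on what is collected, in whom and how it is reported.
- Put the same items to both arms in the existing 12- and 24-month questionnaires: serious events, hospital admissions and drug reactions.
- Tabulate these by arm. Show events reported at nurse contacts separately, since only one arm has those contacts.
- If capture stays one-sided, state that side effects will be described in the nurse arm only and that no between-arm comparison will be made.

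**Tophi**
- Add dated rows at 12 and 24 months, in both arms, for tophus count and calliper diameter of the same index tophus.
- Reconcile the single-contact wording in the Synopsis and the control-arm section with the follow-up items in the regimen table.
- Align the analysis plan's tophus outcome with the protocol endpoint.

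The cost is an amendment, a few questionnaire items and a few minutes at existing assessments. Participants already past 12 months would contribute at 24 months only. The change concerns data collection and reporting; the clinical handling of events stays as it is.
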